# fMRI Substudy Visits for Randomized Subjects

- fMRI substudy participants will be further evaluated at the screening visit for suitability to undergo MRI using the Martinos Center Patient/Volunteer Screening Form.
- Subjects will undergo urine pregnancy tests throughout the study as noted above.
- One hour fMRI sessions will be scheduled at baseline before intervention occurs and at 8 weeks (weeks 0,8)
- Subjects will be administered the IDS-SR, FSS and BFI before each scan (weeks 0, 8)
- A blood draw to measure blood hormone levels on the day of the fMRI scan will occur at both the baseline and 8 week scanning visit.

# fMRI Healthy Control Substudy Visits

Screening visit: A screening visit will take place to determine eligibility for enrollment and ensure that subjects meet inclusion and exclusion criteria. Twenty women with no history of depression or other psychiatric illness will be eligible for the baseline fMRI scan. Screening visit testing will include:

- Complete medical history
- Diagnostic interview with SCID
- Physical examination, including height and weight
- o Morning blood draw for ALT, creatinine, CBC, thyroid stimulating hormone (TSH),

Partners Human Subjects Research Application Version Date: June 1,

Form 2005

free testosterone, FSH, and urine pregnancy test

If a subject is found to be eligible following screening procedures, the subject will be scheduled for the baseline fMRI visit in approximately 1-2 weeks.

# **Baseline fMRI Healthy Control Visit:**

Healthy control subjects will receive one fMRI scan at this visit. Other study procedures include:

- Urine pregnancy test
- Study questionnaires: IDS-SR, FSS and BFI
- A blood draw to measure blood hormone levels on the day of the fMRI scan will occur at both the baseline and 8 week scanning visit.

# Healthy control Visits

**Screening Visit (n=60):** A "Screening Visit" will be conducted to determine eligibility. It is estimated that 60 women will need to be screened to obtain 30 eligible study subjects.

The screening visit will include:

- Abbreviated SCID
- o Medical and psychiatric history including past psychiatric medication use

**Baseline Visit (n=30):** The baseline visit will occur if subjects are found eligible.

Baseline visit will include:

- Psychiatric assessments: MADRS, IDS-SR, CGI-I, S, CPFQ, SF-36, BFI, ESS, FSS, DISF, SAFTEE-SI, CHRT
- Height, weight, vital signs, waist-to-hip ratio, and consumptive habits (alcohol, caffeinated beverages) will be recorded
- Salivary cortisol
- Blood for androgens including total testosterone, free testosterone, neuroactive steroid levels, including allopregnanolone, and cortisol, and other hormones

Describe explicitly the methods for ensuring the safety of subjects. Provide objective criteria for removing a subject from the study, for example, objective criteria for worsening disease/lack of improvement and/or unacceptable adverse events. The inclusion of objective drop criteria is especially important in studies designed with placebo control groups.

**Suicide Prevention:** Suicidal ideation will be assessed by the Beck Suicide Index at each visit. Patients who develop active suicidal ideation, or who are felt by the study clinician to be at high risk for suicide, will be discontinued from the study and referred for hospitalization and further treatment if clinically indicated. In addition, each study subject will be extensively interviewed at each study visit by a highly trained psychiatrist, who not only has extensive experience in the treatment of major depression, but also with these issues in the setting of clinical trial protocols. Patients in research protocols have much more access to psychiatrists than patients in the community, as a study psychiatrist is available by pager 24 hours per day. Moreover, the studies are performed in hospitals in which patients can be immediately admitted, if necessary to ensure safety.

**Drug Safety:** We will measure free testosterone levels every two weeks and decrease the dose to 5 mg (0.5 ml) in any subject with a free testosterone level of more than 2x the upper limit of normal for females at one visit or 1.5x the upper limit of normal at two visits. If the free testosterone level remains above the same limits listed above after the initial dose decrease, the dose will be decreased to 2.5mg (0.25ml). In order to ensure success at raising levels during the

Form 2005

trial, dose increases by 5 mg increments (0.5 ml) daily will be made in subjects in whom the free testosterone level is less than the mean for age at any visit.

**Safety**: Patients will be carefully monitored by clinicians for side effects and potential toxicities with hirsutism and skin assessments. The blood draws will be performed by trained staff who have certificates documenting their ability to draw blood. We are performing a physical examination and routine laboratory tests prior to allowing anyone to enter the randomized phase of the protocol to ensure that subjects are medically stable. Close monitoring of patients throughout the study will ensure that adverse effects from treatment, exacerbation of symptoms, or emergence of suicidality, mania or psychosis will be promptly recognized so that patients can be treated appropriately following study discontinuation. All patients will be instructed on how to contact study clinicians in the case of an emergency. They will also be instructed on how to contact the Acute Psychiatry Service (APS) at MGH and the Patient Assessment Services (PAS) at Butler Hospital, which provide emergent psychiatric care on a 24h/day basis.

Every effort will be made to keep patients in the study. Acceptable reasons for early discontinuation include: 1) request of patient, 2) decision of physician, 3) serious adverse event, 4) worsening of depression requiring hospitalization, 5) emergence of hypomania, mania or psychotic symptoms, 6) pregnancy.

A Data Safety Monitor will review safety data, including adverse events and free testosterone levels twice-a-year and will be available in the interim to consider any urgent matters.

Partners Human Subjects Research Application Version Date: June 1,

Form 2005

Close skin contact with the area of application within an hour of application by a partner or child should be avoided.

AndroFeme contains almond oil. Therefore, individuals with almond allergies may be allergic to this preparation.

**Risks of blood sampling:** Blood sampling is performed in the study, and there is always a very minor risk of infection, bruising, or syncope during a blood draw. There is also the discomfort of having one's blood drawn.

**Discomforts with Questionnaires:** Answering detailed questionnaires may create some inconvenience for subjects.

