#### **RESEARCH DESIGN AND METHODS**

Briefly describe study design and anticipated enrollment, i.e., number of subjects to be enrolled by researchers study-wide and by Partners researchers. Provide a brief summary of the eligibility criteria (for example, age range, gender, medical condition). Include any local site restrictions, for example, "Enrollment at Partners will be limited to adults although the sponsor's protocol is open to both children and adults."

**Study Design:** After antidepressant therapy partial or nonresponse is established by documentation of failure to at least 8 weeks' treatment with an adequately dosed antidepressant therapy, A minimum of 100 subjects study-wide (60 from MGH) with MADRS $\geq$ 12 will enter the double-blind augmentation randomized-placebo-controlled treatment study. 50 of these subjects will be on active study drug and 50 will be control subjects on placebo. Eligible subjects will undergo baseline assessment of symptoms and biological measures and then be randomized to 1 of 2 groups: low-dose physiologic testosterone augmentation by transdermal preparation or placebo.

Antidepressant dose will be held steady during the trial. Outcome measures will examine the antidepressant efficacy of physiologic testosterone treatment (Aim 1), its tolerability (Aim 2) and its effects on 2 specific RDoC symptoms (Aim 3).

**Subject Enrollment:** A total of 330 women will be enrolled study-wide, of which 100 women with antidepressant-resistant MDD and 50 women with no psychiatric history will be eligible study-wide. Study subjects for the depressed population will be women, ages 21-75 with failure to remit following at least 8 weeks antidepressant trial documented by past treatment history.

In addition, 20 healthy controls without

depression will be recruited for the fMRI substudy healthy control population.

Up to 60 postmenopausal women who do not have current or past psychiatric disorders will also be screened to obtain 30 women who will be enrolled

as healthy controls.

Randomized Study Subject Population (n=60)

Inclusion Criteria for Randomized Study Subjects:

- 1. Female, age 21-75, who provide written informed consent
- 2. Free testosterone level no higher than the third quartile of the normal range
- 3. Meet DSM-IV criteria (by SCID) for current Major Depressive Disorder and have MADRS≥12

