# Baseline Visit for the Randomized, Placebo-Controlled, Augmentation Study: Eligible

subjects will undergo baseline testing immediately before the augmentation phase of the protocol. Baseline visit testing will include the following. However, the blood draw will not be repeated if the Baseline visit occurs within 2 weeks of the screening visit.

- Weight, vital signs, waist-to-hip ratio, and consumptive habits (alcohol, caffeinated beverages) will be recorded
- Urine pregnancy test (for premenopausal women only). Postmenopausal is defined as at least one year since last menses and FSH in the postmenopausal range
- Baseline endocrine blood testing: free testosterone, estradiol, neuroactive steroid panel, DHEAS, blood cortisol, late night salivary cortisol and 8 a.m. salivary cortisol
- o Baseline safety blood testing: ALT, creatinine, CBC
- Depression: MADRS, IDS-SR, CGI-I, S
- Cognitive Functioning: CPFQ
- o Persistent/residual symptom assessment: SF-36, BFI, ESS, FSS, DISF
- Safety assessments: SAFTEE-SI, CHRT, and hirsutism and skin assessments
- We will distribute the Study Drug Compliance and Hot Flash Diary or Menopausal Symptom Diary

• We will also collect DNA to be banked for a future exploratory study into whether androgen receptor CAG repeat length moderates androgen-behavior relationships (based on data by Seidmanet *et al.*).

**Follow-up Visits (Placebo-Controlled Augmentation Phase):** Subjects will then be randomized to receive low-dose testosterone or placebo. Follow-up visits will take place at weeks 2, 4, 6 and 8 post-baseline. Follow up visits will include:

- Urine pregnancy test (for premenopausal women only). Postmenopausal is defined as at least one year since last menses and FSH in the postmenopausal range (weeks 2, 4, 6 and 8)
- Free testosterone levels (weeks 2, 4, 6 and 8)
- Skin evaluations to monitor for side effects (weeks 4 and 8)
- Weight and vital signs will be recorded (weeks 4 and 8)
- Waist-to-hip ratio (week 8)
- Depression: MADRS, IDS-SR, CGI-I, S (weeks 2, 4, 6 and 8)
- Cognitive Functioning: CPFQ (weeks 2, 4, 6 and 8)
- Persistent/residual symptom assessment: SF-36, BFI, ESS, FSS, DISF (weeks 2, 4, 6 and 8)
- Safety: SAFTEE-SI, CHRT (weeks 2, 4, 6 and 8)
- Estradiol levels (weeks 2, 4, 6 and 8)
- Salivary cortisol (week 8)
- Medication management sessions (weeks 2, 4, 6 and 8)
- Neuroactive steroid panel (week 8)

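### The +5 mg step-up has no stated exception after a safety reduction, so a woman cut to 2.5 mg can be moved to 7.5 mg, above the 5 mg on which she exceeded the limit

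*Protocol*

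**What the plan says.** Two titration rules stand next to each other in the Protocol's Drug Safety paragraph.

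- **Down.** The instruction is to "decrease the dose to 5 mg (0.5 ml) in any subject" whose free testosterone is "more than 2x the upper limit of normal for females at one visit", or 1.5 times that limit at two visits. "If the free testosterone level remains above the same limits listed above after the initial dose decrease", a second cut takes her to 2.5 mg.
- **Up.** The sentence opens with its purpose, which begins "In order to ensure success at raising levels during the". It then says that "dose increases by 5 mg increments (0.5 ml) daily will be made". The group to which this applies is defined by its hormone level alone: "in subjects in whom the free testosterone level is less than the mean for age at any visit".

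The follow-up schedule for randomized subjects fixes when the rules can act: "Free testosterone levels (weeks 2, 4, 6 and 8". The text supplied gives neither the starting dose nor a maximum dose.

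**The concern.** The second reduction leaves a woman on 2.5 mg, and the only step-up is 5 mg. One step up from 2.5 mg therefore always passes the 5 mg level. The step-up is worded as something that will happen, at any visit, and it does not separate a woman whose level never rose from one who has been reduced because it rose too far. Followed literally, it can undo a safety reduction and go past the dose that prompted it. A clinician who declined the increase would be departing from the written rule.

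**Working it through.** **Inputs.** From the Drug Safety paragraph: reductions to 5 mg and then 2.5 mg, a step-up of 5 mg, and limits of 2 times ULN once or 1.5 times ULN at two visits. From the follow-up schedule: levels at weeks 2, 4, 6 and 8. Treatment lasts 8 weeks, so a change made at week 8 affects no dosing in the trial. The plan gives no figure to reproduce here.

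**The path.**
1. Week 2, above 2 times ULN: dose cut to 5 mg.
2. Week 4, still above 2 times ULN on 5 mg: dose cut to 2.5 mg.
3. Week 6, below the mean for age: 2.5 + 5 = 7.5 mg for weeks 6 to 8.

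7.5 / 5 = 1.5 times the dose on which she exceeded the limit, and 7.5 / 2.5 = 3 times the reduced dose. The starting dose does not enter, provided it is above 5 mg.

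**How many patterns lead there.** Sort each reading into four bands: below the mean, mean to 1.5 times ULN, 1.5 to 2 times, and above 2 times. Three visits give 4 × 4 × 4 = 64 sequences. The text does not say whether the two-visit count restarts after the first reduction. If it restarts, only the path above leads from 2.5 to 7.5 mg by week 6. If it carries over, the sequence above 2 times, 1.5 to 2 times, below the mean does so too.

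**Step-ups after a single reduction.** Here the starting dose matters and has to be assumed. The table counts sequences in which a step-up follows one reduction, and those in which it reaches or passes the lowest dose on which she exceeded a limit.

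| Assumed starting dose | Count restarts | Count carries over |
|---|---|---|
| 7.5 or 10 mg | 9 of 10 | 8 of 9 |
| 15 mg | 1 of 10 | 1 of 9 |
| 20 mg | 0 of 10 | 0 of 9 |

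These are counts of paths, not probabilities.

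**How unusual the week 6 reading must be.** Assume that level = own baseline E + an amount proportional to dose, in multiples of ULN. Assume a mean for age of 0.3 to 0.6, and E from 0 to 0.75. (The inclusion criterion reads "Free testosterone level no higher than the third quartile of the normal range"; 0.75 is an assumed value for that ceiling.) If L is her level on 5 mg:

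- Expected level on 2.5 mg = (L + E) / 2. With L = 2: (2 + 0)/2 = 1.0 to (2 + 0.75)/2 = 1.375.
- Shortfall needed to read below the mean = 1 − mean / expected level: from 1 − 0.6/1.0 = 40% to 1 − 0.3/1.375 = 78%.
- Level if she then takes 7.5 mg in full = 1.5L − 0.5E: from 3.0 − 0.375 = 2.625 to 3.0 times ULN.

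Under carry-over only, with L = 1.5, the expected level on 2.5 mg is 0.75 to 1.125. The shortfall is then 20% to 73%, and the level on 7.5 mg is 1.875 to 2.25 times ULN.

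Missed doses could produce such a shortfall, but on this model not if her own baseline is above the mean for age.

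**The case against.** The strongest objection is that the regimen is not in the text supplied. A reduction to 5 mg presupposes a higher starting dose that is stated nowhere in it, and a limit on re-titration would normally sit with the regimen. A reader might infer that the plan has no dose cap. The documents do not support that, because what was not supplied cannot be called missing. The point survives in a narrower form: a general maximum dose would not block this step unless it were below 7.5 mg. Only a limit that low, or a specific re-titration rule, would answer it.

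Second, the purpose clause points to women whose levels have not risen, and a woman twice above the limit is not one of them. That is probably the intent. The operative words do not say so, and the remedy would only write it down.

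Third, the path is narrow. It needs a week 6 reading far below expectation, it lasts at most two weeks, and free testosterone is measured again at week 8. Clinician monitoring, discontinuation by physician decision and a Data Safety Monitor available between the twice-yearly reviews all remain. A reader might infer that reduced women are unprotected. That does not follow. However, physician decision is listed as a ground for stopping early, not for withholding a step-up.

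Fourth, the level figures rest on assumed kinetics and reference values. That is correct, and they serve only to show how unusual the path is.

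**Conclusion.** The concern holds as a minor gap in one dosing sentence. As written in the text supplied, the step-up can take a woman from 2.5 mg to 7.5 mg, which is 1.5 times the dose on which she exceeded the limit. This needs only a starting dose above 5 mg and a literal reading of the step-up sentence. Its frequency cannot be derived from the documents and is probably low.

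A reader might also infer that any step-up after a safety reduction returns the woman to the dose that caused it. That does not hold in general. After a single reduction it depends on the unstated starting dose: most patterns at an assumed 7.5 or 10 mg, one at 15 mg, none at 20 mg. Nor do the documents tie two weeks at 7.5 mg to any harm. Confidence is medium, because the regimen text might already contain a limit.

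**What to change.** Add one sentence to the Drug Safety paragraph: after any safety reduction, no step-up may take the subject to or above the lowest dose on which her free testosterone exceeded a safety limit. This closes the path by construction, whatever the starting dose and however the two-visit count is read. If the regimen already contains such a limit, a cross-reference is enough. It would also help to say whether the two-visit count restarts after a reduction.

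No new test, visit or threshold is needed. The cost falls on the step-up's own aim. With 5 mg increments, women at 2.5 mg, and women cut to 5 mg from 10 mg or less, would get no further step-up and might stay below the mean for age. Women cut to 5 mg from a dose above 10 mg could still go to 10 mg.

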Testosterone Antidepressant Augmentation in Women

NCT01783574

Version Date: February 1, 2017

Study Endpoints and Data Analysis

Specific Aim 1: We will investigate in women with partial/nonresponse to antidepressant therapy whether low-dose testosterone augmentation leads to a significantly greater reduction in depressive symptoms compared to a placebo group over an 8-week period.

Experimental Strategy and Endpoints: To investigate the effects of physiologic testosterone augmentation on antidepressant therapy partial/nonresponse, 50 women with partial/nonresponse to antidepressant therapy randomized to testosterone augmentation and 50 to placebo in the 8-week randomized, double-blind placebo controlled study delineated in the "Overall Protocol", will be compared. Depressive symptom endpoints will be measured at baseline and weeks 2, 4, 6 and 8. The primary endpoint will be MADRS score in weeks 2-8.

• These data will determine the effects of low-dose testosterone augmentation on depressive symptoms in women with partial/nonresponse to antidepressant therapy.

Data Analysis: For Aim 1, the data will be analyzed using a mixed-effect linear regression model. The randomization will be stratified by site, estrogen use, and one vs. more than one adequate antidepressant therapy trial. The model will specify a baseline MADRS score and baseline non-responder vs. partial responder as covariates and then an "on treatment score," which is the score from weeks 2 through 8. The following will be entered into the model as covariates: baseline non-responder vs. partial responder, one vs. more than one adequate antidepressant therapy trial, baseline free testosterone level, baseline age and site (MGH or Butler Hospital). The on treatment score will have a fixed treatment effect and a random patient effect. We will examine interactions between menopausal status and effect to determine whether menopausal status moderates the treatment effect. This model is the same as in a repeated measures analysis of (co)variance with the assumption of compound symmetry. Our pilot data shown in Figure 2 fits this model. Specifically, based on our preliminary data, we expect a rapid improvement in depression severity by 2 weeks followed by maintenance of the effect of the subsequent 6 weeks. One advantage of this method is that it allows us to use data from patients who drop out early despite our plans to obtain follow-up data on all patients randomized and analyze all data obtained. A subject who drops out in the middle of the study will add data to the analysis. The drop-out rate should be low due to the relatively short duration of the study and the anticipated low side effect profile, the latter as confirmed in our pilot study in this population in which we had no drop-outs over the 8-week period. This model assumes that the drop-outs are missing at random. We will attempt to obtain 8-week observations on all patients, including drop-outs. Sensitivity analysis will be performed to determine whether our conclusions are sensitive to this assumption (185). Secondary analyses will determine whether the response of depressive symptoms to testosterone is affected by baseline androgens and neuroactive metabolites (including free testosterone level, DHEAS, and 3α -diol), estradiol, blood cortisol, late night cortisol and 8 a.m. salivary cortisol, and changes in the same variables over the 8-week period. Pre-treatment free testosterone level will be entered into the model as a covariate along with a treatment baseline interaction. Other covariates that will be explored will be age, menopausal status, baseline MADRS score, change in estradiol levels, change in free testosterone levels and BMI. As a secondary

endpoint, we will determine the 8-week remission rate in an exploratory analysis. Remission will be defined as MADRS score<10. Comparison of ratios of remitters to the total number of study participants in the testosterone and placebo groups will be compared using a Fisher Exact test. Another secondary endpoint will be effects of testosterone on functional measures. The same methods as described for MADRS score analyses will be used to analyze functional measures, including the SF-36.

For Aim 1B, the primary analysis will be to determine whether the neuroactive metabolite of testosterone, 3a-diol, is an important determinant of the effects of testosterone on our primary endpoint, MADRS score. We expect to be able to distinguish the effect of 3a-diol from the effect of an increase in serum free testosterone levels because we expect the relative levels of the two hormones will differ, i.e. we expect that some study subjects will convert a greater proportion of testosterone to the 3α -diol metabolite than other study subjects. Analyzing the effect of both free testosterone and 3α-diol on the outcome (MADRS score) by linear regression, we hope to determine the relative importance of each hormone as a determinant of outcome. It is conceivable that both will correlate with the MADRS score, simply reflecting absorption of testosterone, and it is also possible that one will correlate with MADRS score, and the other will not. For instance, if the coefficient of the metabolite 3α -diol in a regression of outcome on 3α-diol and free testosterone is large while that of free testosterone is small, then we would conclude that the active factor is 3a-diol rather than free testosterone. If the correlation coefficient between the two of these is large, we would not have data to make a determination of which is active.

Specific Aim 2: We will investigate in women with partial/nonresponse to antidepressant therapy whether adjunctive low-dose testosterone is safe and welltolerated in women with partial/nonresponse to antidepressant therapy. Experimental Strategy and Endpoints: To investigate whether adjunctive physiologic testosterone is safe and well-tolerated over the 8-week protocol, we will compare rates of adverse events in subjects randomized to testosterone augmentation to those receiving placebo using the SAFTEE-SI. These endpoints will also include increases in ALT and hirsutism and skin assessment scores and decreases in HDL cholesterol. The primary endpoint will be adverse effect rate.

• These data will determine whether adjunctive physiologic testosterone is safe and well-tolerated in women with relative partial/nonresponse to antidepressant therapy.

Data Analysis: Rates for each adverse effect will be computed by group. Differences between treatment groups in dropout rates will be examined using a Fisher's Exact test, though every effort will be made to retain subjects through the 8-week course. If a trend (p < .10) indicative of differential dropout is detected, a more detailed survival analysis will be completed to illustrate the timing and magnitude of these differences.

Specific Aim 3: Low-dose testosterone augmentation improves persistent/residual symptoms in women with antidepressant-resistant depression.

Experimental Strategy and Endpoints: To investigate the effects of low-dose testosterone augmentation on fatigue and energy in women with antidepressant-resistant depression, the 50 women with antidepressant-resistant depression

randomized to testosterone augmentation and 50 to the placebo arm of the 8-week randomized, double-blind placebo controlled study delineated in the "Overall Protocol", will be compared. Energy/fatigue and sexual function/libido endpoints will be measured at baseline and weeks 2, 4, 6 and 8. The primary endpoint will be BFI score weeks 2-8.

• These data will determine the effects of low-dose testosterone augmentation on fatigue and sexual function in women with antidepressant-resistant depression.

Data Analysis: The data will be analyzed using a mixed-effect linear regression model, using methods and assumptions as in Specific Aim 1 Data Analysis, above.

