- Currently treated with an antidepressant (1st, 2nd or 3rd trial in current episode), that has been taken at an adequate dose for at least eight weeks with sufficient source documentation to confirm high level of confidence in treatment details (using the MGH ATRQ). Current treatment may include a combination therapy as long as the subject has not exceeded three failed trials in the current episode.
- 5. Persistent depression symptom burden of the same dose of the currently (ineffective) antidepressant therapy, evidenced by MADRS≥12.

Exclusion Criteria for Randomized Study Subjects:

- 1. Serious suicide or homicide risk, as assessed by evaluating clinician
- 2. Unstable medical illness including cardiovascular, hepatic, renal, respiratory, endocrine, neurologic
- 3. Substance use disorder active within last six months, or clinical suspicion of ongoing substance use disorder at the discretion of the study clinician at time of screening based on history and/or laboratory results.
- 4. Any history of psychotic features, bipolar disorder, or primary obsessive compulsive disorder, as assessed by SCID
- 5. Untreated hypothyroidism. If treated hypothyroidism, change in levothyroxine dose within the prior 3 mos
- 6. Use of androgens, including testosterone, DHEA and methyltestosterone, within the prior three months
- 7. Any investigational psychotropic drug within the last 30 days
- 8. In the judgment of the study clinician, unlikely to be able to participate safely throughout the study period (three or more episodes of self-harm in the past year, documented history of poor treatment adherence, or frequent missed appointments (>50%) in the past year)
- 9. Alanine aminotransferase (ALT) > 3x upper limit of normal or creatinine> 3x upper limit
- 10. History of a hormone-responsive cancer
- 11. History of testosterone abuse
- 12. Almond allergy (AndroFeme contains almond oil)
- 13. History of hypercalcemia or thromboembolism
- 14. Women who are breastfeeding
- 15. Pregnant women, women who desire to become pregnant, or women of child bearing potential who are not using a medically accepted means of contraception (to include condom, diaphragm, spermicide, intrauterine device, tubal ligation, or partner with vasectomy)

Additional Exclusion Criteria for Randomized study subjects in fMRI Substudy Only (n=20)

Exclusion criteria for the fMRI substudy participants include routine MRI exclusion criteria as listed below:

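### Estrogen use is a randomisation stratum but not a covariate in the primary MADRS model; if it is prognostic beyond the listed covariates, the test is slightly conservative and loses a little power

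*SAP*

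**What the plan says.** The SAP's Specific Aim 1 Data Analysis states: "The randomization will be stratified by site, estrogen use, and one vs. more than one adequate antidepressant therapy trial". The same paragraph gives the primary model's covariates: baseline MADRS, non-responder versus partial responder, and then "one vs. more than one adequate antidepressant therapy trial, baseline free testosterone level, baseline age and site (MGH or Butler Hospital". Two of the three strata are there. Estrogen use is not, and no reason is given.

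Related variables appear nearby, but none is the stratum:

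- A secondary analysis asks whether response depends on baseline androgens and metabolites, then "estradiol, blood cortisol, late night cortisol and 8 a.m. salivary cortisol, and changes in the same variables over the 8-week period".
- Menopausal status is examined as a moderator of the treatment effect.
- An exploratory list begins: "Other covariates that will be explored will be age, menopausal status, baseline MADRS score, change in estradiol levels".

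The stratum is not empty by design. The Protocol's exclusion criteria for randomised subjects bar "Use of androgens, including testosterone, DHEA and methyltestosterone, within the prior three months" but list no exclusion for estrogen use.

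The model is used again. For functional outcomes, "The same methods as described for MADRS score analyses will be used to analyze functional measures, including the SF-36". For the BFI, the Specific Aim 3 primary endpoint, the data are analysed "using methods and assumptions as in Specific Aim 1 Data Analysis, above".

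**The concern.** Stratified randomisation makes the arms more alike on the stratum, so the treatment estimate varies less from trial to trial. The analysis gets the benefit only if the stratum is in the model. If it is left out, its variance stays in the residual and the reported standard error describes a less precise design than the one that was run.

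What is at stake is precision in a comparison of 50 versus 50 women. The confidence interval would be a little wider than necessary, the actual type I error a little below nominal, and power a little lower. This happens only if estrogen use predicts on-treatment MADRS over and above baseline MADRS, responder status, number of trials, free testosterone, age and site.

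**Working it through.** **Plan's own figure.** The supplied text gives no power, alpha, effect size or SD for the primary comparison, so there is nothing to reproduce.

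**Inputs from the documents.** 50 women per arm; three strata (eight cells if each is binary); the covariates listed above; a fixed treatment effect and a random patient effect. With complete data this model gives the same treatment estimate as an analysis of covariance on patient means.

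**Assumed inputs.**

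- Two-sided alpha 0.05
- Residual SD of patient means: 7 points
- Treatment effect: 4 points (about 79% power with estrogen use in the model)
- Share of users p: 10%, 20% or 30%
- User/non-user difference d: 2 or 4 points
- Share a of estrogen use explained by the other covariates: 0 or 0.3
- Permuted blocks of 4

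**Step 1, closed form.** The ratio of interval widths, estrogen use omitted over included, is

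ratio = sqrt(1 + d² p(1−p)(1−a) / SD²)

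For d = 4, p = 0.2, a = 0: 16 × 0.16 / 49 = 0.0522, and sqrt(1.0522) = 1.026.

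| d | a | p = 10% | p = 20% | p = 30% |
|---|---|---|---|---|
| 2 | 0 | 1.004 | 1.007 | 1.009 |
| 4 | 0 | 1.015 | 1.026 | 1.034 |
| 4 | 0.3 | 1.010 | 1.018 | 1.024 |

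The assumed SD matters little. At d = 4 and a = 0, the range over p is 1.020-1.046 for SD 6 and 1.009-1.021 for SD 9.

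**Step 2, simulation.** 40,000 trials per setting, 100 women, eight strata, planned covariates, with and without estrogen use. Unlike the closed form, this includes the degree of freedom spent and the imperfect balance left by incomplete blocks.

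- No overlap (a = 0), d = 4: ratio 1.013, 1.025 and 1.033 for p = 10, 20 and 30%; power loss 0.8-2.2 points. At 20% users, power is 0.774 without and 0.789 with the covariate. Type I error with it omitted is 4.5-4.8%.
- No overlap, d = 2: power loss 0.2-0.5 points; type I error 4.9-5.0%.
- Age explains 30% of estrogen use, d = 4: intervals 0.7-2.2% too wide; power loss 0.5-1.2 points.
- Age explains 30%, d = 2: excess width −0.1 to 0.4%; power change about zero (−0.1 to 0.1 points).
- Not prognostic (d = 0): adding the covariate widens intervals by 0.1-0.3% and costs 0.1-0.3 power points.

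**Step 3, cross-check by another route.** At d = 4, p = 0.2, a = 0, estrogen use explains 2.56 / (49 + 2.56) = 0.05 of the residual patient variance. A normal approximation gives an SE ratio of 1/sqrt(0.95) = 1.026 and an actual alpha of 0.044. Where the adjusted model has 80% power, the model without the stratum has 78.5%, a loss of 1.5 points, the same as in Step 2. Separate simulations showed no material bias (below 0.005 SD).

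**The case against.** The strongest reply is that the test is valid as written and no documented harm exists. Nothing in the documents says that estrogen use is prognostic once the other covariates are in, and every magnitude above is assumed. That is right, and it limits the point to a small, conditional loss of efficiency.

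The second reply is that age will absorb part of the effect. Eligibility is "Female, age 21-75, who provide written informed consent", so estrogen use may track age. The contraceptive methods named in the Protocol's exclusion criteria include none containing estrogen. The list may not be exhaustive, but it hints that users would be mostly postmenopausal. As a check, take ages uniform over 21-75, users only above 50 and d = 4. Excess interval width is then about 1.3-2.1% with age in the model for 10-30% users, and 1.3-1.8% if menopausal status also enters. Both lie inside the 0.7-2.2% range, so this reply stands as a reason to put most weight on the overlap figures. It does not remove the point.

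A reader might also say that estradiol or menopausal status stands in for the stratum. Neither is the same as estrogen use, and neither is in the primary covariate list. Change in estradiol is measured after randomisation and cannot replace a design factor.

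In the other direction, a reader might infer that leaving out a stratum biases the result or inflates false positives. It does neither: the error runs the other way. Nor do the documents support a large power loss. A loss of about 7 points would need estrogen use to explain 20% of the residual variance, which is unlikely with age and baseline MADRS already in the model.

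**Conclusion.** The point holds as a minor, optional improvement. That one of the three strata is missing from the primary model, and so from the SF-36 and BFI models, is clear from the text. The consequence is conditional: if estrogen use is prognostic beyond the listed covariates, the standard error is slightly too large and a little power is lost.

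For a 4-point difference, the best-supported size is roughly 1-2% of interval width and about 1 power point, allowing for overlap with age. The no-overlap case is the upper end of the range. For a 2-point difference there is practically nothing to gain. These sizes rest on the assumed share of users, residual SD, treatment effect and block size, none of which the documents give. The direction does not depend on those values.

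**What to change.** Add estrogen use (yes/no, as recorded for stratification) to the covariate list of the Aim 1 MADRS model, before unblinding. The SF-36 and BFI analyses already adopt the Aim 1 methods, so the change carries over to them without further wording. Naming it in advance also avoids an argument over adding it once results are known.

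The cost is one line of SAP text and one degree of freedom. No new data are needed, because estrogen use must be known at randomisation to serve as a stratum. If it proves not to be prognostic, the price is the 0.1-0.3% of interval width and 0.1-0.3 power points shown in the working.
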